13.0 Non-Study Treatments

13.1 Prior and Concomitant Medications

All medications (including prescription and over-the-counter medications, supplements, and herbal products) taken from 28 days before Baseline (Day 1) through the TOC visit will be recorded on the eCRF. Only the use of antifungal medications, antibiotics for any reason or medications to treat an AE will be recorded after the TOC visit through the last study visit (FU). Start and stop dates of concomitant medications taken during antifungal therapy will be recorded on the eCRF. Prior and concomitant medications will be reviewed and recorded at all study visits.

Certain concomitant medications must be administered with caution or close monitoring as described in Appendix A [Section 21.0](#).

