14.15 Subject Diary Completion

Subjects will complete their diaries from Day 1 through the TOC visit. The subject diaries will include the VSS Scale so that subjects can rate their vulvovaginal symptoms. Subjects will record the date of study medication dosing, daily vulvovaginal symptoms, other medical concerns or complaints and concomitant medications used. Subjects will be instructed to return their subject diaries at the TOC visit (Day 10).

After the TOC visit, subjects will not be required to complete a diary but will be instructed to call the site immediately if they experience new or worsening signs/symptoms or medical concerns/complaints. The site will also determine if any signs/symptoms or other medical concerns/complaints recorded on the diary should be reported as AEs. The information from the subject diary will be included as part of the eCRFs.

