14.20 Prior and Concomitant Medication Review

All medications (including prescription and over-the-counter medications, supplements and herbal products) taken from 28 days before Baseline (Day1) and through the TOC visit will be recorded on the eCRF. Only the use of antifungal medications, antibiotics for any reason or any other medication to treat an AE will be recorded after the TOC visit through the last study visit (FU). Start and stop dates of concomitant medications taken during antifungal therapy will be recorded on the eCRF. Prior and concomitant medications will be reviewed and recorded at all study visits.

See [Section 13.0](#) for prohibited medications, medications to be administered with caution and further details for non-study treatments.

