16.0 Safety Assessments and Monitoring

16.1 Definition of an Adverse Event

An AE is any untoward medical occurrence associated with the use of a drug in humans, whether or not considered drug related. An AE can therefore be any unfavorable and unintended sign (including an abnormal laboratory finding), symptom or disease temporally associated with the use of a study drug/study intervention, whether or not related to the study drug/study intervention.

Any laboratory abnormality that is deemed to be clinically significant in the opinion of the investigator will be considered an AE and should be recorded in the eCRF, whether or not it is related to the study drug.

Stable chronic conditions that are present prior to clinical trial enrollment and do not worsen are not considered AEs and will be accounted for in the subject's medical history.

The following can be considered AEs:

- An exacerbation of a pre-existing illness
- An increase in frequency or intensity of a pre-existing episodic event or condition
- A condition detected or diagnosed after the initiation of treatment with study medication, even though it may have been present prior to the start of the study
- Continuous persistent disease or symptoms present at Baseline that worsen after signing the informed consent or following the initiation of treatment with study medication

The following are **not** considered AEs:

- Medical or surgical procedures (e.g., surgery, endoscopy, tooth extraction or transfusion); the condition that leads to the procedure is an AE
- Pre-existing disease or conditions present or detected at the start of the study that do not worsen
- Situations where an untoward medical occurrence has not occurred (e.g., hospitalizations for cosmetic surgery or elective surgery or social/convenience admissions)

- The disease being studied or signs or symptoms associated with the disease, unless more severe than expected for the subject's condition or a worsening of the disease being studied

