18.7 Efficacy

18.7.1 Efficacy Assessments

The primary efficacy endpoint of the study is the percentage of subjects with clinical cure (complete resolution of signs and symptoms) at the TOC visit. Secondary efficacy endpoints include the percentage of subjects with mycological eradication (negative fungal culture) at the TOC visit, the percentage of subjects with both clinical cure and mycological eradication at the TOC and FU visits, the percentage of subjects with continued clinical

response (continued absence of signs and symptoms) at the FU visit and the time to resolution of signs and symptoms after initiation of study drug. The percentage of subjects with a negative KOH test at the TOC visit, the percentage of subjects who are free of signs and symptoms at the FU visit, the percentage of subjects by *Candida* species infection at Baseline, the percentage of isolates susceptible to SCY-078 and fluconazole, the percentage of subjects with clinical cure (complete resolution of signs and symptoms) at TOC by *Candida* species and the percentage of subjects with mycological eradication (negative fungal culture) at TOC by *Candida* species will be evaluated as exploratory endpoints.

The following treatment outcome definitions will be used for the assessment of efficacy:

Clinical Outcome

- **Clinical cure:** Complete resolution of signs and symptoms of vulvovaginal infection without need for further antifungal treatment. Specifically, for complete resolution, any sign or symptom should be absent (score = 0) by the TOC visit.
- **Clinical failure:** No response to therapy or incomplete resolution of signs and symptoms or need for additional vulvovaginal or systemic antifungal therapy. If the subject receives or self-administers topical drug therapy for the treatment of vulvovaginal irritation/pruritus such as topical analgesic or corticosteroid after completing treatment with the study drug and before the TOC visit, the subject is considered a clinical failure.
- **Continued Clinical Response:** Continued absence of signs and symptoms of vulvovaginal infection at the FU visit in subjects who achieved clinical cure at the TOC visit.
- **Free of Signs and Symptoms:** Absence of signs and symptoms of vulvovaginal infection at the FU visit.
- **Mycological Outcome**
- **Mycological eradication:** A subject with negative culture (no growth) for *Candida* species.
- **Mycological persistence:** A subject with a positive culture for *Candida* species.

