11.8.2 Secondary Efficacy Endpoints

The secondary efficacy endpoints include the following:

- The percentage of subjects with Mycological Eradication (negative fungal culture) at the TOC and FU visit.

Mycological Eradication is defined as a subject with negative culture (no growth) for *Candida* species. Conversely, Mycological Persistence is defined as a subject with positive culture for *Candida* species.

- The percentage of subjects with both Clinical Cure and Mycological Eradication at the TOC visit. If either component assessment is missing, the subject will be considered as missing for this endpoint and imputed as non-responders in the analysis
- The percentage of subjects with both absence of signs and symptoms and Mycological Eradication at the FU visit. If either component assessment is missing, the subject will be considered as missing for this endpoint and imputed as non-responders in the analysis
- The percentage of subjects with Continued Clinical Response at the Follow-up (FU) visit, defined as continued absence of signs and symptoms in subjects who achieved Clinical Cure at the TOC visit
- The time to resolution of signs and symptoms after initiation of study drug, defined as time (days) from first dose of study medication to the first resolution of signs and symptoms. Subjects who discontinued early will be censored at the last available assessment.

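### Topical symptom relief is a failure before test of cure, but between test of cure and follow-up it has no endpoint rule and only partial recording, so a suppressed mild recurrence can pass as sustained response

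*Protocol*

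**What the plan says.** **Before TOC.** Protocol 18.7.1 and SAP 11.8.1 treat topical drug therapy for vulvovaginal irritation or pruritus, with analgesics and corticosteroids as examples, as failure if it is used "after completing treatment with the study drug and before the TOC visit, the subject is considered a clinical failure".

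**At FU.** Protocol 18.7.1 defines Continued Clinical Response as "Continued absence of signs and symptoms of vulvovaginal infection at the FU visit in subjects who achieved clinical cure at the TOC visit". SAP 11.8.2 has it "defined as continued absence of signs and symptoms in subjects who achieved Clinical Cure at the TOC visit". Free of Signs and Symptoms, an exploratory endpoint, is defined on the FU scores alone. Neither endpoint has a medication condition in either document.

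**Recording after TOC.** Protocol 13.1: "Only the use of antifungal medications, antibiotics for any reason or medications to treat an AE will be recorded after the TOC visit". Protocol 14.20 repeats the limit: "Only the use of antifungal medications, antibiotics for any reason or any other medication to treat an AE will be recorded after the TOC visit". Up to TOC, all medications are recorded, including over-the-counter products.

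**What counts as an AE.** Protocol 16.1 lists among non-AEs "The disease being studied or signs or symptoms associated with the disease, unless more severe than expected" for the subject. The same sentence also excepts a deterioration of the studied disease.

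**Diary.** Protocol 14.15: "After the TOC visit, subjects will not be required to complete a diary". Subjects are instead told to telephone the site at once if complaints appear or get worse.

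**The concern.** The plan already accepts the principle: a zero score reached with the help of a topical relief product is not a valid response. It applies that principle up to TOC and then drops it, at the point where the question becomes whether the response lasts. Recording narrows at the same visit, so the information needed to apply the principle later may not exist.

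The FU clinical endpoints matter because Protocol 7.1 motivates the drug partly by recurrence after fungistatic azoles and by the hope of better longer-term outcomes. Only a subject who relapses can have a relapse masked. If the share masked is similar in all arms, the error is larger where relapse is more frequent, and a true difference between arms shrinks.

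**Working it through.** **Step 1: the two intervals side by side**

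| | End of study drug to TOC | TOC to FU |
|---|---|---|
| Failure rule for topical relief | Yes (Protocol 18.7.1, SAP 11.8.1) | None |
| Medications recorded | All | Antifungals, antibiotics, AE treatment (13.1, 14.20) |
| Daily diary | Yes | No (14.15) |
| Topical vaginal corticosteroid | Prohibited (13.2, Appendix A) | Prohibited |
| Topical analgesic | Not named as prohibited | Not named as prohibited |
| KOH and central culture | At TOC | At FU (14.9) |

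**Step 2: one subject traced through the rules.** She scores 0 on all six items at TOC and is a cure. Mild itch returns a few days later. It is not reported as an AE, and she uses an over-the-counter topical analgesic. At FU all six items are again 0.

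- Under both documents she has Continued Clinical Response and is Free of Signs and Symptoms.
- The missing-as-failure rule in SAP 8 does not act, because nothing is missing.
- If her FU culture is positive, she fails the FU composite (SAP 11.8.2) but still counts as Continued Clinical Response.
- If it is negative, nothing collected distinguishes her from a genuine sustained responder.

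**Step 3: size.** The documents give no relapse rate, cure rate or masking share and no sample-size calculation, so there is no plan figure to reproduce. Inputs:

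- From the documents: n = 30 per arm (Protocol 18.1, SAP 6); two-sided 5% level, unadjusted (Protocol 18.0, SAP 10.1).
- Assumed: TOC cure c = 0.60 (range 0.50-0.70); relapse among cured subjects r = 0.10-0.30; share of relapses masked at FU s = 0.10-0.50.

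One misclassified subject moves the rate by:

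- 100/30 = 3.3 points of the arm;
- 100/21 = 4.8 to 100/15 = 6.7 points of TOC cures (21 and 15 being 70% and 50% of 30).

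Overstatement among TOC-cured subjects = [1 - r(1 - s)] - (1 - r) = r x s:

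| r | s = 0.10 | s = 0.25 | s = 0.50 |
|---|---|---|---|
| 0.10 | 1.0 | 2.5 | 5.0 |
| 0.20 | 2.0 | 5.0 | 10.0 |
| 0.30 | 3.0 | 7.5 | 15.0 |

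(percentage points)

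Subjects per arm = n x c x r x s:

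- 30 x 0.60 x 0.20 x 0.25 = 0.9 (3 points of the arm);
- 30 x 0.60 x 0.30 x 0.50 = 2.7 (9 points of the arm).

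**Step 4: effect on a comparison.** Suppose relapse is 30% in one arm and 10% in the other, with s = 0.25 in both. Observed sustained response among the cured is 1 - 0.30 x 0.75 = 0.775 and 1 - 0.10 x 0.75 = 0.925. The observed difference is 15 points against a true 20.

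Fisher's exact test on invented counts: 22/30 versus 14/30 gives p = 0.064. Moving one comparator subject to failure gives 22/30 versus 13/30, p = 0.035. With 20/30 versus 15/30 the same move changes p only from 0.29 to 0.19. One subject can matter at this arm size, but need not.

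**The case against.** The strongest reply is that several planned routes already catch such cases.

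- **AE route.** Treatment of an AE is recorded after TOC, and a deterioration of the disease is an AE. For a subject who scored 0 at TOC, returning itch may reasonably be judged one.
- **Contact with the site.** Subjects are told to call, and unscheduled visits include sign and symptom ratings, medication review and AE monitoring (Protocol 14.15, Table 2).
- **Signs as well as symptoms.** The FU endpoints also need investigator-rated edema, erythema and excoriation to be absent. An analgesic would not obviously clear those, so high masking shares are less plausible.
- **Corticosteroids.** Vaginal corticoids are prohibited throughout. Known use can be logged as a deviation (SAP 11.2), and interfering medication is an example of a reason for exclusion from the PP population (SAP 7).
- **Mycology.** KOH and culture are done for everyone at FU.

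All of this stands and narrows the gap. It does not close it. A mild recurrence with symptoms alone, not judged an AE and not telephoned in, leaves no required record if the product is an analgesic. The FU medication review does not help, because 13.1 and 14.20 define what that review records. Continued Clinical Response does not require a negative culture.

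A reader might infer more: that topical use after TOC is never recorded, that masked relapses can never be found, or that no later analysis could help. The documents do not support this. The AE exception stands in the recording sentence itself, and FU culture permits a useful sensitivity analysis from planned data.

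A reader might also want the pre-TOC window to open at the first dose. That would fail a subject on the primary endpoint for relief use during the dosing days, while still symptomatic from the baseline episode, even with zero scores at TOC. The present window leaves those days out, and nothing in the documents shows that to be a mistake. The narrower wording point is that a subject who stops study drug early may not literally complete treatment. Her medications are recorded through TOC, so no data are lost and a clarification is enough.

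**Conclusion.** The concern holds in a limited form. From TOC to FU the plan has no rule for topical symptomatic products in Continued Clinical Response (secondary) or Free of Signs and Symptoms (exploratory), and it records them only when they treat an AE. A TOC-cured subject with a mild recurrence suppressed by a non-AE product can count as a sustained responder, and her use may not be identifiable.

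The TOC-to-FU gap does not touch the primary endpoint. The FU composite is largely protected, because a culture-positive case already fails it.

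The size cannot be known from the documents. Each such subject is worth 3.3 points of a 30-subject arm. The 1-to-15-point range among TOC-cured subjects rests wholly on the assumed relapse and masking rates, and the signs requirement makes its upper end less likely. The shrinking of arm differences further assumes similar masking shares across arms. The study is exploratory and not powered for formal comparisons, which limits the consequence; but use that was never recorded cannot be reliably recovered later, and the change is cheap.

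**What to change.** 1. **Recording (Protocol 13.1, 14.20).** Add any topical vulvovaginal product, with its indication, to the medications recorded from TOC through FU.
2. **Endpoint rule (Protocol 18.7.1, SAP 11.8.2 and 11.8.3).** Count subjects who used such a product for vulvovaginal irritation or pruritus between TOC and FU as non-responders for Continued Clinical Response and Free of Signs and Symptoms.
3. **Sensitivity analysis (SAP 11.9.2).** Repeat the Continued Clinical Response analysis with a negative FU culture as an added requirement. This uses data already planned and is worth having even if the recording cannot be changed.
4. **Pre-TOC wording.** Keep the exclusion of the dosing days. At most, clarify that completing treatment means the last dose taken, so that early stoppers are covered.

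Cost: one more medication category at FU, short wording edits and one extra analysis. FU response rates will be slightly lower. As under the existing pre-TOC rule, some subjects who used a product for irritation unrelated to candidiasis will be counted as non-responders; the recorded indication lets these be described.

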13.2 Prohibited Medications

Medications specifically not permitted in the exclusion criteria ([Section 11.2](#)) include the following:

- Non-study systemic or topical antifungal therapy
- Topical vaginal corticoids
- Vaginal contraceptives
- Other investigational drug(s)
- Strong CYP3A4/5 inhibitors, select moderate CYP3A4/5 inhibitors, CYP3A4/5 inducers, select CYP2C8 substrates and select P-gp substrates.

See [Section 21.0 \(Appendix A\)](#) for the full list of prohibited medications.

13.3 Medications to be Administered with Caution and Monitored as Appropriate

The following medications must be administered with caution and must be monitored as appropriate:

- Moderate CYP3A4/5 inhibitors (except for the select prohibited moderate CYP3A4/5 inhibitors)
- CYP3A4 substrates, including but not limited to sirolimus, tacrolimus and warfarin
- Organic anion-transporting polypeptide 1B3 (OATP1B3) substrates

See [Section 21.0 \(Appendix A\)](#) for the full list of medications to be administered with caution.

13.4 Study Restrictions

There are no additional study restrictions other than those described in [Sections 11.2](#) (Exclusion Criteria), [Section 12.2](#) (Dietary Requirements) and [Section 13.2](#) (Prohibited Medications).

14.0 Study Procedures

The following sections provide a description of the individual study procedures to be performed during the conduct of the study. Detailed schedules of study assessments are provided in the Schedule of Visits and Procedures in Table 2.

14.1 Informed Consent

Every study subject must provide written informed consent at Screening, prior to participating in any Screening evaluations or any other study activities (see [Section 19.3](#)).

14.2 Assignment of Subject Number

At Screening, all subjects who have signed an ICF will receive a unique subject identification (ID) number, which will consist of a 4-digit subject ID number that will be composed of a 2-digit site number followed by a 2-digit sequentially assigned subject number starting at 01, at each site. For instance, the first subject from site 01 will have 0101 as her assigned subject number and the subsequent subject from this site will have 0102 as her assigned subject number. The first subject from site 02 will have 0201 as her assigned subject number and the subsequent subject from this site will have 0202 as her assigned subject number. The subject numbers assigned to eligible subjects will be recorded in the eCRF. This number will be unique to each subject and will be used to identify the subject throughout the study. This number is different from the treatment bottle number.

Subjects who are screen failures or who are not eligible for randomization will be recorded as such in the eCRF. For subjects who sign an ICF (i.e., are assigned a subject number) but are NOT assigned a treatment assignment number because they do not meet all of the inclusion/exclusion criteria, the applicable Screening visit pages of the eCRF will be completed. The criteria that were not met for randomization will be documented in the eCRF.

14.3 Inclusion and Exclusion Criteria

All inclusion and exclusion criteria will be reviewed at Screening and at Baseline (Day 1) to ensure that the subject qualifies for the trial.

14.4 Medical History and Demographics

During the Screening visit, a complete medical history for the prior year will be recorded for each subject. The medical history will include previous and current medical diagnoses and major surgical procedures. Subject demographics such as age, sex, race and ethnicity will also be collected.

14.5 Abbreviated Physical Examination

An abbreviated physical examination, including general appearance and an overall examination of body systems, will be conducted at Screening and at the TOC visit.

14.6 Urine Pregnancy Test

A urine pregnancy test will be performed at Screening and at unscheduled visits (if needed) by the local laboratory for all subjects of childbearing potential. The pregnancy test results will be reviewed at Baseline (Day 1) before starting/dispensing study drug.

14.7 Safety Laboratory Tests

Safety laboratory tests will be performed by a qualified central laboratory. Safety laboratory tests will also be performed at the Screening, TOC visit and at unscheduled visits, if needed. If indicated, these may be done more frequently as follow up to a laboratory abnormality.

The following laboratory parameters will be determined:

Hematology

- White blood cell (WBC) count
- Red blood cell (RBC) count
- Platelet count
- Hemoglobin
- Hematocrit
- Differential WBC count will include percentages for lymphocytes, monocytes, eosinophils and basophils, and absolute counts for neutrophils, lymphocytes, atypical lymphocytes, monocytes, eosinophils and basophils.

Blood Chemistry

- Glucose
- Albumin
- Sodium
- Potassium
- Alkaline Phosphatase
- Creatinine
- Total creatine phosphokinase (CPK)
- Aspartate aminotransferase (AST/SGOT)
- Alanine aminotransferase (ALT/SGPT)
- Gamma glutamyl transferase (GGT)
- Bilirubin (total, direct and indirect)
- Total protein

14.8 Vulvovaginal Samples for Identification of Other Pathogens and Vaginal pH

A vulvovaginal specimen will be obtained and assessed locally at the Screening visit to rule out bacterial vaginosis and *Trichomonas*. Testing for *N. gonorrhoea*, *Chlamydia* or *Herpes* virus will also be conducted by a qualified laboratory (local or central laboratory), if clinically indicated. Vaginal samples will be tested for bacterial vaginosis, *Trichomonas*, *N. gonorrhoea*, *Chlamydia* or

Herpes virus at unscheduled visits only if needed. Vulvovaginal specimens will also be obtained at the Screening visit for local vaginal pH determination.

Procedures for collecting and shipping vulvovaginal samples are described in the laboratory manual.

